#### **5.4.1 Data Collection and Follow-up for Withdrawn Subjects**

Patients must document in a letter asking not to use the data collected and formalize the withdrawal. Otherwise, data up until withdrawal will be available for analysis.

#### **5.5 Early Termination Visits**

This may be due to the subjects' own choice or the investigator's decision. If the investigator makes the decision, subjects will be contacted and reasons for study termination will be thoroughly explained.

### **6 Statistical Plan**

#### **6.1 Sample Size and Power Determination**

The sample size is based on a previously successful study with the same purpose [1], and an anticipated 15% drop-out/withdrawal rate. Significant decrease in the dynamic strain in OnabotulinumtoxinA and AbobotulinumtoxinA were determined at day 4, 14, and 90 post intervention compared to baseline. We are increasing the patient population to account for a potential increase drop out due to the number of follow-up visits.

#### **6.2 Statistical Methods**

The primary analysis will be done using chi-squared testing and Fischer's exact test for categorical variables, where applicable, and the paired t-test for continuous variables. Analysis is preformed blinded at the end of the study. There is no interim analysis.

#### **6.3 Control of Bias and Confounding**

Block randomization will be employed to assign subjects into each study arm. 40 blocks consisting of 4 assignments per block will be used in sequence until study enrollment is complete. The injecting physician will be blinded to which neuromodulator is assigned at the time of injections prevent any underlying bias.

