## **3 Investigational Plan**

### **3.1 General Design**

This study is a randomized controlled trial in which patients will be randomly assigned into one of four groups: those receiving onabotulinumtoxinA (Botox, Allergan, Irvine, California), abobotulinumtoxinA (Dysport, Ipsen Biopharmaceuticals Inc. Cambridge, MA), incobotulinumtoxinA (Xeomin, Raleigh, NC) or prabotulinumtoxinA (Jeuveau, Evolus, Newport Beach, California). Each patient will receive FDA approved dosages in which they are assigned in to treat rhytids within the glabella, as per FDA approved indications. All injections will be performed by a blinded single trained physician ([name]) according to a preset injection plan per FDA approved administration guidelines. Prior to injection patients will be imaged with 3-dimensional photogrammetry. All pre-procedure images will be evaluated for absolute strain performing two types of facial animation: 1) relaxed, and 2) frowning. Subjects will return Day 3, 30, 90, and 180, post intervention for re-imaging with the same expressions. Strain will be calculated using the same metrics.

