### **3.2 Allocation to Interventional Group**

Subjects will be randomized to either the prabotulinumtoxinA abobotulinumtoxinA, incobotulinumtoxinA or onabotulinumtoxinA groups. Subjects will be randomized in a one to one fashion using block randomization.

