### ***4.2 Total Number of Subjects and Sites***

140 patients will be enrolled from at a single location, the Hospital of the University of Pennsylvania.

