##### **5.2.1 Visit 1 (sometimes referred to as the baseline visit)**

Visit 1 involves screening, consent, baseline imaging to measure dynamic strain, randomization, intervention. The subject will be photographed using 3D imaging with multiple facial animations. All pre-procedure images will be evaluated for absolute strain performing two types of facial animation: 1) relaxed, 2) frowning. Following the baseline images, subjects will complete a FACE-Q questionnaire and then randomized to one of the four neuromodulators onabotulinumtoxinA (Botox, Allergan, Irvine, California), abobotulinumtoxinA (Dysport, Ipsen Biopharmaceuticals Inc. Cambridge, MA), incobotulinumtoxinA (Xeomin, Raleigh, NC) or PrabotulinumtoxinA (Jeuveau, Evolus, Newport Beach, California) according to a preset injection plan per FDA approved administration guidelines. The injector will be blinded to the neuromodulator assigned to the subject via randomization at the time of injection in order to decrease any underlying bias during drug administration. The syringes will be documented and prepared by appropriately trained staff.

CONFIDENTIAL

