## **8 Study Monitoring, Auditing, and Inspecting**

### ***8.1 Study Monitoring Plan***

This study will be closely monitored by the PI and the project manager. The PI will be participating and the data will be collected by the PI and one other study team member from the patient's EMR. The study team member will enter the data into the REDCap and the project manager will monitor the entry to verify the compliance with respect to the protocol, data collection and source documents.

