## **9.4 Informed Consent Process / HIPAA Authorization**

All subjects for this study will be provided a consent form describing this study providing sufficient information for subjects to make an informed decision about their participation in this study. This consent form will be submitted with the protocol for review and approval by the IRB for the study. The formal consent of a subject, using the IRB-approved consent form, must be obtained before that subject undergoes any study procedure. The subject, or legally acceptable surrogate, must sign the consent form, and the investigator-designated research professional obtaining the consent. Subjects will be consented by the study Principal Investigator, or appropriate designee, in a room we have selected in which to perform consent, which is located outside of the clinic. Potential subjects will review the consent form in detail with the person designated to consent (either PI or CRC) and have the ability to take the consent home for further review.

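### One fixed, printed block size of 4 for four equal arms, with no allocation concealment described: up to 35 of 140 allocations would be predictable to anyone who knew the earlier ones

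*Combined protocol and SAP*

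**What the plan says.** **Allocation.** Section 3.1 says that "patients will be randomly assigned into one of four groups", and section 3.2 adds that "Subjects will be randomized in a one to one fashion using block randomization". Section 4.2 sets the size and setting: "140 patients will be enrolled from at a single location". Section 6.3 gives the blocking rule: "40 blocks consisting of 4 assignments per block will be used in sequence until study enrollment is complete". No stratification is described, so there is one list, followed in order of enrolment.

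**Masking.** Section 5.2 labels the study single blinded without saying who is blinded. Section 5.2.1 says: "The injector will be blinded to the neuromodulator assigned to the subject via randomization at the time of injection". Sections 3.1 and 6.3 repeat that the injector is blinded. Section 6.2 says that the analysis is done blinded at the end of the study. No masking is stated for anyone else who takes part in enrolment.

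**Who does what.** Section 9.4: "Subjects will be consented by the study Principal Investigator, or appropriate designee"; it later names the PI or CRC. Section 8.1: "the data will be collected by the PI and one other study team member", from the medical record. Section 5.2.1 has trained staff, not further identified, prepare and document the syringes. It also places randomization after consent, baseline imaging and the FACE-Q.

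**Not stated.** The plan does not say who generates the list, who holds it, how the next assignment is hidden until it is needed, or whether those who consent subjects may know earlier assignments.

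**The concern.** The smallest possible block for four equal arms is 4, and it is the most predictable. Here it is also the only size, and anyone with the protocol can read it. With a single list at one site, counting randomized subjects gives the position within the block.

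Someone who knows the earlier assignments and also screens or consents could foresee some of the next ones. Screening, consent and randomization all take place at Visit 1. A foreseen product could therefore influence whether a candidate is enrolled, or when. The primary objective in section 2.1 compares the four products, and the first secondary endpoint in section 3.4.2 is a between-product contrast in strain. Selective enrolment would bias such contrasts, and would bias self-reported FACE-Q scores in the same way. No planned analysis could reliably undo that.

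**Working it through.** **Inputs.** Four arms (3.1), equal allocation (3.2), 140 subjects at one site (4.2), blocks of 4 used in sequence (6.3). The 15% drop-out in section 6.1 plays no part, because predictability concerns subjects at the moment of allocation.

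**The plan's own figures.** 40 × 4 = 160 list positions, against 140 subjects. Since 140 / 4 = 35, enrolment uses exactly 35 blocks and leaves 5 spare. The rule runs only until enrolment is complete, so 160 against 140 is not an inconsistency.

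**Certain allocations, all earlier ones known.** Each block of 4 contains each product once, so the fourth position is determined by the first three. That is 1 per block: 35 × 1 = 35 of 140, or 25%.

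**Average correct guess, all earlier ones known.** The best guess at positions 1 to 4 is right with probability 1/4, 1/3, 1/2 and 1.

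- Per block: 1/4 + 1/3 + 1/2 + 1 = 2.083
- Rate: 2.083 / 4 = 52.1%
- Over 35 blocks: 35 × 2.083 = 72.9 of 140
- By chance: 1/4 × 140 = 35 of 140, or 25%

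**Certain allocations, earlier ones only partly known.** The plan does not say how much anyone sees. Assume that each earlier assignment is seen independently with probability q. The fourth is certain only if all three before it were seen, so the expected number is 35 × q³.

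| q (assumed) | q³ | Certain allocations |
|---|---|---|
| 1 | 1 | 35 |
| 0.9 | 0.729 | 25.5 |
| 0.75 | 0.422 | 14.8 |
| 0.5 | 0.125 | 4.4 |

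**Alternatives, all earlier assignments known.** Fixed sizes are by exact enumeration. Mixed sizes are by simulation (400 trials of 140), with each size equally likely and a guesser who knows the possible sizes but not the current one.

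| Block sizes | Certain, share | Certain, of 140 | Average correct guess |
|---|---|---|---|
| 4 (as planned) | 25.0% | 35 | 52.1% |
| 8 | 14.3% | 20 | 47.0% |
| 12 | 10.0% | 14 | 44.1% |
| 4 and 8, mixed | 7.4% | about 10 | about 49% |
| 4, 8 and 12, mixed | 3.6% | about 5 | about 46% |

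Mixing sizes removes most of the certainty but little of the average guessability.

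**The case against.** Predictability does harm only if someone who influences enrolment knows the earlier assignments. A reader might infer that the plan gives the consenting person that knowledge, since the PI may obtain consent (9.4) and also collects data from the medical record (8.1). The documents do not support that step. Nothing says that the record shows the product, that the PI or CRC sees assignments, or that either prepares syringes. Section 7.7 also allows data not normally in the record to go on case report forms. This objection stands: the most that can be said is that access is not barred.

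A reader might also infer that the injector is the only person masked. Section 6.2 blinds the analysis as well. Nor do the documents show a route by which the injector learns past products; every product is drawn up as 0.5 mL in a single syringe with a 30-gauge needle. The injector's name is removed from the public text, so it cannot be told whether the PI is the injector.

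Section 5.2.1 already randomizes after consent and baseline procedures. That is sound, and it protects against an assignment that is disclosed too early. It does not protect against one that is foreseen, because a predicted fourth allocation is known before consent is sought.

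Finally, varying the block size moves the average guess only from 52% to about 46%. That is correct, and it is why concealment should lead the fix.

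**Conclusion.** The point holds as a gap in concealment that the choice of block makes worse. The fixed, printed size of 4 follows directly from sections 3.1, 3.2, 4.2 and 6.3. The absence of any described concealment comes from reading the whole plan, and it is not explained by removed text.

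The size is a ceiling of 35 certain allocations in 140 (25%) and a 52% average correct guess against 25% by chance. It rests on one unstratified list, a known block position and full knowledge of earlier assignments. Under the assumed partial knowledge, about 26, 15 or 4 allocations would be certain. The documents do not show that predictable allocations would be exploited, or that anyone who consents subjects has the information to do so.

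This is a cheap improvement to the design, not an error that invalidates it.

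**What to change.** Amend section 6.3 in this order of importance.

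1. State that the list is generated and held by someone who does not screen, consent or enrol subjects.
2. State that each assignment is released only to the staff who prepare syringes, after eligibility, consent and baseline procedures are recorded. The order in section 5.2.1 already places randomization there; what is missing is who receives the assignment. State also that those who consent subjects are kept from past assignments.
3. Replace the fixed blocks of 4 with randomly varying sizes, for example 4, 8 and 12. Take the sizes out of the protocol and hold them in a restricted randomization file.

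**Cost.** One new computer-generated list and a wording change. Blocks of 4 divide 140 exactly and would give 35 per arm. With varying sizes, enrolment may stop mid-block. A block of 12 holds 3 slots per arm, so arms could differ by up to 3 subjects.

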##### **6.3.1 Baseline Data**

Baseline and demographic characteristics will be summarized by standard descriptive statistics (including mean and standard deviation for continuous variables such as age and standard percentages for categorical variables such as race).

##### **6.3.2 Analysis of Primary Outcome of Interest**

The primary analysis will be done using chi-squared testing and Fischer's exact test for categorical variables, where applicable, and the paired t-test for continuous variables.

CONFIDENTIAL

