## Study Summary

Title	A Randomized Prospective Evaluation of Four Injectable Neuromodulators in the Glabella Area: Randomized Controlled Trial
Short Title	Glabella 4 Toxin Study
IRB Number	849045
Protocol Number	NCT05167864
Methodology	Randomized Control Trial
Study Duration	18 months
Study Center(s)	Single-center.
Objectives	To quantify the dynamic strain of four commonly available neuromodulators injected in the glabellar area over time as well as correlate patient satisfaction to the change in dynamic strain over time.
Number of Subjects	Approximately 140
Main Inclusion and Exclusion Criteria	
Inclusion criteria:
 

1) Women ages 30-65

2) No neuromodulator treatment within 12 months

3) Have not undergone cosmetic procedures to the upper face above the malar region (cheekbone area).

 
Exclusion:
 

1) Men

2) Patients who have previously been treated with a neuromodulator<12 months

3) Over 65 or under 30 years of age

4) Those with a prior known condition that affects facial animation (such as stroke, palsy),

5) Cannot be actively taking blood thinners,

6) Presence of eye ptosis

7) Autoimmune disease

CONFIDENTIAL

Intervention	Randomization to one of four neuromodulator glabellar injections: 1) onabotulinumtoxinA 2) abobotulinumtoxinA 3) incobotulinumtoxinA 4) PrabotulinumtoxinA
Statistical Methodology	Descriptive statistics will be used to describe variables of interest. Fischer's exact test and Chi-square will be used to compare categorical variables, and linear regression will be used for continuous variables.
Data and Safety Monitoring Plan	PI will oversee the study, protocol, and data monitoring and storage.

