### ***3.4 Study Endpoints***

#### **3.4.1 Primary Study Endpoint**

The primary endpoint is to quantify the change in dynamic strain of the glabella area after injection of four neuromodulators using 3D facial imaging measurements over time.

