### ***4.1 Duration of Study Participation***

The duration of study participation is a minimum of 180 days. Subjects will receive injections on day-1, and follow up imaging and analysis occurs on day 3, 30, 90 and 180 post intervention.

The overall study duration is estimated 12- 18 months. It may take approximately 6 months to enroll all subjects and complete initial imaging and procedures, 7 months for follow up imaging, and 4-5 months for data analysis. Each individual subject's participation time in the study will consist of the duration of the initial imaging session (approximately 20 minutes), procedure (15 minutes), follow up imaging (20 min).

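### A baseline-to-visit paired t-test leaves a woman out at each visit she misses and cannot use her earlier images there, so with 15% expected loss the points over time rest on different women and the late change could be biased

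*Combined protocol and SAP*

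**What the plan says.** Section 6.3.2, repeating section 6.2, gives "the paired t-test for continuous variables" as the primary analysis of continuous data. Section 6.2 adds "Analysis is preformed blinded at the end of the study", so there is one final analysis. The Study Summary differs: "linear regression will be used for continuous variables".

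The primary endpoint in section 3.4.1 is the change in glabellar dynamic strain "using 3D facial imaging measurements over time". Section 4.1 fixes the times: "follow up imaging and analysis occurs on day 3, 30, 90 and 180 post intervention".

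On loss, section 6.1 assumes "an anticipated 15% drop-out/withdrawal rate" and gives one response: "We are increasing the patient population to account for a potential increase drop out due to the number of follow-up visits". Section 5.4.1 says that, unless a woman asks in writing that her data not be used, "data up until withdrawal will be available for analysis".

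The plan defines no pairs for the t-test, no analysis set, no handling of a missed visit, no repeated-measures model and no missing-data sensitivity analysis.

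**The concern.** A paired test at a visit needs two images per woman. If one is baseline and the other is that visit, a woman who leaves after Day 90 counts at Days 3, 30 and 90 and disappears at Day 180. Her Day 90 strain is the best available evidence on her Day 180 strain, but the Day 180 test has no way to use it.

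Two things follow. The step from Day 90 to Day 180 mixes real waning of effect with a change in who is measured. And the Day 180 mean is unbiased only if those who left would have had the same average change as those who stayed. If leaving is related to how well the product is still working, that fails. Durability is what the later visits measure, so this is where an error would matter most. A larger sample narrows the interval around the estimate but does not move the estimate.

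**Working it through.** **Inputs from the documents.** 140 women (4.2); four products with equal allocation (3.2); follow-up at Days 3, 30, 90 and 180 (4.1); 15% loss overall, not split by visit or product (6.1).

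**Inputs not in the documents.** Alpha, power, effect size, SD, within-woman correlations and the reasons for loss. The bias figures below are therefore illustrations.

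**Step 1: the stated sample size.** It cannot be derived, because its ingredients are absent. Working backwards, 140 × (1 − 0.15) = 119, and 119 / 0.85 = 140. So 140 is consistent with about 119 evaluable women, but the plan does not state that base.

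**Step 2: available pairs.** 140 / 4 = 35 per product. 140 × 0.15 = 21 lost, leaving 119, or 119 / 4 = 29.75 per product. If loss is monotone, pairs fall from at most 140 at the earliest visit to about 119 at Day 180. If instead 15% missed each visit independently (a different assumption), 140 × 0.85⁴ = 73 women would contribute to all four points.

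**Step 3: size of a possible bias at Day 180.** Assume equal SDs of 1 at every visit, correlation *r* between baseline and each later visit, correlation 0.7 between Days 90 and 180, and 15% missing at Day 180. Let the odds of loss rise by a factor OR per SD of Day 90 strain level. Let *m* be the amount by which mean Day 90 strain among those who stay falls below that of all women. Because baseline and Day 180 are both linearly related to Day 90,

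bias in mean change = −(0.7 − *r*) × *m*.

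Numerical integration of the logistic loss model gives *m*:

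| OR per SD | *m* | size of bias, *r* = 0.3 | *r* = 0.5 | *r* = 0.7 |
|---|---|---|---|---|
| 1 | 0 | 0 | 0 | 0 |
| 1.5 | 0.060 | 0.4 × 0.060 = 0.024 | 0.2 × 0.060 = 0.012 | 0 |
| 2 | 0.098 | 0.039 | 0.020 | 0 |
| 3 | 0.142 | 0.057 | 0.028 | 0 |
| 5 | 0.182 | 0.073 | 0.036 | 0 |

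Simulation of the same scenario gave 0.025 to 0.075 SD at *r* = 0.3 and 0.011 to 0.035 SD at 0.5. Rounding outwards, the ranges are 0.02 to 0.08 and 0.01 to 0.04 SD. An estimate that uses the observed baseline and Day 90 values of every woman was within 0.003 SD of the truth throughout.

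**Step 4: scale.** The SE of a paired mean in one product is √(2(1 − *r*)/29.75). At *r* = 0.3 this is √(1.4/29.75) = 0.217 SD, so the largest bias in the table is 0.073 / 0.217 = 0.34 of an SE. At *r* = 0.5 it is 0.036 / 0.183 = 0.20 of an SE.

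**Step 5: differences between products.** If loss works the same way in every product, the bias cancels. If the OR were 1.5 for one product and 5 for another at *r* = 0.3, the difference would be biased by 0.073 − 0.024 = 0.049 SD.

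**Step 6: would the Study Summary's method close the gap?** No. Ordinary regression fitted visit by visit also omits women without that visit's value.

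**The case against.** Much of the case against a stronger reading stands.

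- A reader might infer that a woman who misses one visit is dropped altogether. The documents do not say so. She is left out only where her image is missing, and section 5.4.1 keeps her earlier data. Dropping her everywhere would make the sets of women identical at all visits.
- A reader might infer that women select themselves out when the effect fades, so that the late effect is overstated. Nothing in the plan links leaving to waning. Section 5.4 also allows discontinuation by the investigator or after an adverse event. Section 9.2 pays women after the last follow-up visit, which would encourage attendance, although section 10.3 says there are no payments. If women with a lasting effect are the ones who skip Day 180, the sign reverses. It also reverses in Step 3 if *r* exceeds 0.7.
- A reader might want to quote the bias as a sizeable share of the treatment effect. The plan gives no effect size or SD, so no such percentage can be supported.
- The baseline-to-visit pairing is inferred. The plan does not define the pairs, and the Study Summary names another method.
- The primary objective in section 2.1 compares products, and Step 5 shows little bias there.

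These points limit the size and certainty of the concern. They do not supply a rule for missed visits, and they do not let a paired test use the retained images.

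**Conclusion.** The concern holds as a weakness of the stated method. With the loss the plan itself expects, a baseline-to-visit paired t-test uses different women at different visits, discards relevant earlier images at each missed visit, and is open to bias that extra enrolment cannot remove.

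The likely size is modest: on the assumptions above, no more than about a third of a standard error for one product's Day 180 change, and nil if loss is unrelated to strain. The direction is not established. These figures rest on assumed correlations, equal SDs, and loss that depends on Day 90 strain level.

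It should be corrected because the remedy is cheap and also supplies the between-product comparison that section 2.1 and the first secondary endpoint require, which a within-woman paired test cannot give. The documents do not support a claim that the trial's late results will be biased.

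**What to change.** Replace the paired t-tests in sections 6.2 and 6.3.2, and bring the Study Summary into line, with one likelihood-based repeated-measures model:

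- **Data:** all observed images from all randomised women, analysed as assigned, stated as the primary analysis set.
- **Terms:** product, visit, product by visit and baseline strain, with unstructured within-woman covariance over Days 3, 30, 90 and 180.
- **Product differences:** taken from this model at each visit.
- **Within-product change:** defined explicitly, because it cannot simply be read from a model of strain level adjusted for baseline. Either model change from baseline with centred baseline strain, or include baseline as a response in a constrained longitudinal model.
- **Reporting:** missing images by product and visit, with reasons. Keep the paired result on observed pairs as a secondary display.
- **Sensitivity:** an analysis for loss that depends on unobserved strain, for example a delta adjustment that shifts the missing values by increasing amounts. An analysis of observed pairs or completers does not test this.

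The cost is protocol wording and a standard model, with no new visits, images or women. The model assumes that data are missing at random given observed strain. That can fail, for instance if the effect wears off unseen between Days 90 and 180, but it is weaker than what the paired t-test assumes.
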